7.4. Subject Compliance and Adverse Event Monitoring

7.4.1. Adverse Event Monitoring

Adverse events (AEs) must be reported on the Adverse Event Form (AEF). Adverse events that will be monitored include urticaria, anaphylaxis, respiratory compromise, cardiac events, seizure, and death. These events will be monitored in the first 3 months after surgery. Complete clearance of SF is expected within 72 hours, and associated adverse events, if any, are anticipated within that timeframe. After discharge from the hospital, any reporting of adverse events will rely upon participants contacting the research team prior to the scheduled 3 month follow up. Nausea and vomiting will not be included as an adverse event as these symptoms are expected outcomes from surgery.

If adverse events occur, the first concern will be the safety and welfare of the patient. Appropriate medical intervention will be made. Any adverse events observed by the Investigator or reported by the patients will be recorded in the appropriate section of the patient's Case Report Form (CRF) as well as on an Adverse Event Form.

The Investigator must categorize each AE by degree of harm to the patient (mild, moderate, or serious), and the relationship to study device (not related, possibly, probably, or definitely) in the Adverse Event Form. Adverse events observed will be captured on the Adverse Event Follow-up Form and the CRF until such time the adverse event is reported as resolved, or for the course of the study if the event does not resolve.

A serious adverse event includes any prolong hospitalization, and any event that is life-threatening, results in permanent impairment of a bodily function or permanent damage to a body structure, or an event that necessitates medical or surgical intervention to preclude such permanent impairment or permanent damage.

Changes in any chronic condition or disease that are consistent with natural disease progression are not considered AEs and will not be recorded on an AE CRF.

Medical treatment related to any adverse events will not be paid for by the study, Mayo Clinic, or the Sponsor. Patients and their insurance will be billed for any treatments or encounters associated with an adverse event.

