7.4.2. Adverse Event Reporting

Any serious adverse events, whether unanticipated or not, and whether or not ascribed to study device, will be communicated promptly to Carl Zeiss Meditec Inc and to the IRB. These reports must be confirmed in writing within 5 days of the occurrence.

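### The serious adverse event definition names neither death nor a new hospital admission, and *serious* is also the top harm grade, so the trigger for prompt reporting is ambiguous

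*Protocol*

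**What the plan says.** Protocol section 7.4.1 lists the events to be tracked: "Adverse events that will be monitored include urticaria, anaphylaxis, respiratory compromise, cardiac events, seizure, and death". On the period it says: "These events will be monitored in the first 3 months after surgery". Once the patient has left hospital, "any reporting of adverse events will rely upon participants contacting the research team prior to the scheduled 3 month follow up".

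The same section grades each event: "The Investigator must categorize each AE by degree of harm to the patient (mild, moderate, or serious"). Two paragraphs later it defines the serious category by outcome: "A serious adverse event includes any prolong hospitalization, and any event that is life-threatening, results in permanent impairment of a bodily function". Permanent damage to a body structure follows, and the list closes with "or an event that necessitates medical or surgical intervention to preclude such permanent impairment or permanent damage".

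Section 7.4.2 sets the reporting duty: "Any serious adverse events, whether unanticipated or not, and whether or not ascribed to study device, will be communicated promptly" to the sponsor and the IRB. On timing it adds: "These reports must be confirmed in writing within 5 days of the occurrence".

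The protocol has no other definition of a serious adverse event. The Adverse Event Form is not among the three appendices.

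**The concern.** One word decides whether an event goes promptly to the sponsor and the IRB, and section 7.4.1 uses that word in two ways. In one paragraph it is the highest of three levels of harm; in another it is a category defined by outcome. The protocol does not say which of the two section 7.4.2 refers to.

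The outcome list is also incomplete for the period it serves. Once the surgical stay is over it can no longer be prolonged, and the hospital event that remains possible is an admission, which the list does not name. Death is missing from the list as well, although it is one of the monitored events.

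Two things are at stake. First, two investigators who both follow the text could handle the same readmission differently, so sponsor and IRB might not hear of it promptly. Second, the data on the primary safety endpoint (section 3.6.10) would be collected on a scale that mixes how intense an event was with whether it met a reporting criterion. That cannot be untangled at analysis, because the category is fixed when the form is completed.

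**Working it through.** The point contains no figure, so the check is one of text. It takes the outcome list and the harm scale in 7.4.1 as the two possible triggers for 7.4.2 and runs typical events through both. The examples are constructed from the monitored events; they are not taken from the protocol.

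| Event | Meets a listed outcome? | Harm grade available | Prompt report under 7.4.2? |
|---|---|---|---|
| Urticaria of limited intensity that extends the surgical stay | Yes, prolonged stay | Mild or moderate is a fair grade | Yes by outcome, no by grade |
| Readmission for a self-limited seizure: no threat to life, no permanent impairment, no intervention to prevent it | No | Moderate or serious, by judgement | No by outcome, uncertain by grade |
| Readmission needing intervention to prevent permanent damage | Yes, last clause | Serious is a fair grade | Yes |
| Intense but brief reaction meeting no listed outcome | No | No level above moderate except serious | No by outcome; by grade, reported or under-graded |
| Death | Not named; would ordinarily be read as life-threatening | Serious | Yes in practice |

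Three results follow.

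1. If the outcome list is the trigger, the second row falls outside it. If the harm grade is the trigger, the second row depends on the individual investigator. On neither reading is that readmission clearly reportable.

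2. The first and fourth rows show that grade and outcome can disagree in both directions. The scale has no severe level, and 7.4.1 describes no separate seriousness item.

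3. The other reporting routes do not supply promptness for the second row:
   - The investigation team meets quarterly (section 3.8).
   - Case report forms go to the sponsor, with no prompt deadline stated (section 3.9).
   - The sponsor's progress reports to the IRB are at least yearly (Appendix 1).
   - The route with a 10-working-day limit covers only unanticipated adverse device effects (Appendix 2).

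   Section 7.4.2 is meant to reach further than that last route, since it applies whether or not the event is attributed to the device.

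The protocol gives neither a length of stay nor a readmission rate. The number of events in the second row among the planned 90 patients therefore cannot be calculated.

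**The case against.** The best defence is that the definition is open. It says what a serious event includes, so an item left off the list is not thereby excluded, and section 1.1 commits the study to Good Clinical Practice and ICH guidelines. An investigator acting sensibly would report a readmission for a seizure. Fluorescein is expected to clear within 72 hours, with any associated events in that time, so few drug-related events should arise after discharge. The form is not shown and may already hold a seriousness item. Every recorded event reaches the sponsor eventually, so only timing is in question.

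Much of this stands, and it rules out several stronger conclusions that a reader might draw:

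- *That deaths would go unreported.* Death is expressly monitored, a fatal event would ordinarily be read as life-threatening, and no one would grade it below serious. The omission is a drafting defect.
- *That the whole period after discharge is uncovered.* Threat to life, permanent impairment or damage, and intervention to prevent them all apply after discharge. Only admissions that meet none of these are in doubt.
- *That severity cannot be tabulated.* The three harm levels can be tabulated. What is lost is the separation of severity from seriousness.
- *That a mild event prolonging the stay must be coded at the top grade.* The text does not say so. It leaves the link between grade and definition open.

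What does not stand is the claim that open wording settles the matter. It leaves the decision to each investigator, under a rule that requires written confirmation within 5 days. Nor does the 72-hour statement help: the protocol chose a 3-month window, and 7.4.2 does not depend on attribution to the device.

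**Conclusion.** The concern holds in a limited form. The definition in 7.4.1 omits death and new or repeat admission, and *serious* serves both as a harm grade and as the reporting category. The trigger in 7.4.2 is therefore ambiguous for readmissions in the 3-month window that meet none of the listed outcomes, and severe but non-serious events have no grade of their own.

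The affected readmissions are a narrow subset, and for them the issue is promptness of reporting. The merged scale reaches further, since every graded event is recorded on it. No efficacy endpoint or analysis changes.

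The conclusion assumes that the Adverse Event Form follows the section's text and has no separate seriousness item. If it has one, the second limb is largely met in practice, though the protocol should still say so, and the first limb is unaffected.

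**What to change.** In section 7.4.1, name death and initial or repeat in-patient hospitalization in the serious adverse event definition, alongside the existing criteria. Grade severity as mild, moderate or severe. Record seriousness on the Adverse Event Form as a separate yes/no item, with the criterion that was met. In section 7.4.2, state that prompt reporting is triggered by that yes/no item.

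The cost is a small form change, an amended definition with its matching cross-reference, and possibly a few more prompt reports among 90 patients. No dose, procedure or patient care is touched.

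The change does not cure a separate limit: after discharge the team learns of events only if participants make contact, so a readmission may stay unknown until the 3-month visit however it is defined.

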7.4.2. Adverse Event Reporting

Any serious adverse events, whether unanticipated or not, and whether or not ascribed to study device, will be communicated promptly to Carl Zeiss Meditec Inc and to the IRB. These reports must be confirmed in writing within 5 days of the occurrence.

7.5. Packaging

FS usually comes in a package of twelve vials. **Ak-fluor®** (fluorescein injection, USP) 10% is supplied in a single-use 5 mL glass vial with a gray bromobutyl serum siliconized stopper and orange flip-off cap. It contains a sterile, dark-reddish orange solution of fluorescein sodium.

7.6. Receiving, Storage, Dispensing and Return

7.6.1. Receiving of Drug Supplies

FS is currently available in the local pharmacy in the hospital. The supply during the course of this study will be coordinated as part of the regular drug supply in the OR

7.6.2. Storage

AK-Fluor® (fluorescein injection, USP) 10% will be temporarily storage at 2°- 25°C (36°- 77°F) in the sterile court for study cases in the OR.

7.6.3. Dispensing of Study Drug

The drug is currently available in the local pharmacy of the hospital. The Saint Mary's Hospital OR Pharmacy Managers will be informed of the need for drug in the OR during the IRB approval process. The OR pharmacy will dispense the drug to the anesthesiologist or certified nurse anesthetist participating in the case.

7.6.4. Return or Destruction of Study Drug

Fluorescein residual in a vial that was not used during the study procedure will be destroyed.

8. Clinical Investigation and Documentation

8.1. Requirements before Starting the Clinical Investigation

- CIP written and signed
- Approval of ethics/IRB committee obtained

8.2. Training and Information for Clinical Investigators

The sponsor shall provide training for clinical investigators covering:

- YE560 fluorescence features available on the microscope
- YE560 module set up
- Turn on/off the YE560 module during surgery
- Contrast agents and clinical workflows
- Recording videos and capturing pictures during surgery
- Software operation
- Reviewing, managing and backing up procedure data (e.g. videos pictures)

8.3. Investigator and Sponsor File Maintained

- Clinical Investigation Plan
- CV for each clinical investigator
- Ethics committee approval and correspondence
- Correspondence with authorities required by national legislation
- Agreement between investigators and sponsor
- Insurance certificates
- Informed consent forms and information provided to subjects
- Case report forms
- Forms for reporting adverse events and adverse device effects
- Names and contact addresses of the monitor

8.4. Final Report

- Signed principal clinical investigator
- Available to all clinical investigators and the ethics committee
- Includes thorough identification of device
- Description of the methodology
- Design of clinical investigation
- Summary of the Clinical Investigation Plan and any deviations
- Data analysis with any statistical analyses (if applicable)
- Critical appraisal relating to aims of the investigation

APPENDIX 1

Sponsor's Obligations

Responsibilities of Sponsors

General responsibilities of Sponsors

Sponsors are responsible for providing investigators with the information they need to conduct the investigation properly.

Specific responsibility of Sponsors

1. *Obtaining agreements.* A Sponsor shall obtain from each participating Investigator a signed agreement that includes:

A statement of the Investigator's commitment to:

I. Conduct the investigation in accordance with the agreement, the investigational plan, this part and other applicable FDA regulations, and conditions of approval imposed by the reviewing IRB or FDA;

II. Supervise all testing of the device involving human subjects; and

III. Ensure that the requirements for obtaining informed consent are met (21CFR Part 50).

Sponsor Records

A Sponsor shall maintain the following accurate, complete, and current records relating to an investigation for a period of 3 years after completion of the study:

1. All correspondence with an Investigator, an IRB, or FDA, including required reports.

2. Records of shipment. Records of shipment shall include the name and address of the consignee, type and quantity of device, date of shipment, and serial number.

3. Signed Investigator agreements.

4. Records concerning adverse device effects (whether anticipated or unanticipated) and complaints.

5. Any other records that FDA requires to be maintained by regulation or by specific requirement for a category of investigation or a particular investigation.

Sponsor Reports

A Sponsor shall prepare and submit the following complete, accurate, and timely reports:

1. *Unanticipated adverse device effects.* A Sponsor who conducts an evaluation of an unanticipated adverse device effect shall report the results of such evaluation to FDA and to all reviewing IRBs and participating Investigators within 10 working days after the Sponsor first receives notice of the effect. Thereafter the Sponsor shall submit such additional reports concerning the effect as FDA requests.

2. *Withdrawal of IRB approval.* A Sponsor shall notify FDA and all reviewing IRBs and participating Investigators of any withdrawal of approval of an investigation or a part of an investigation by a reviewing IRB within 5 working days after receipt of the withdrawal of approval.

3. *Withdrawal of FDA approval.* A Sponsor shall notify all reviewing IRBs and participating Investigators of any withdrawal of FDA approval of the investigation, and shall do so within 5 working days after receipt of notice of the withdrawal of approval.

4. *Progress reports.* At regular intervals, and at least yearly, a Sponsor shall submit progress reports to all reviewing IRBs.

APPENDIX 2

Investigator's Agreement and Obligations

Responsibilities of Investigators

General responsibilities of Investigators

An Investigator is responsible for ensuring that an investigation is conducted according to the signed agreement, the investigational plan and applicable FDA regulations, for protecting the rights, safety, and welfare of subjects under the Investigator's care, and for the control of devices under investigation. An Investigator also is responsible for ensuring that informed consent is obtained in accordance with 21 CFR part 50.

Study staff will meet on a quarterly basis to debrief and assess progress, with email contact in the interim as needed. Meeting outcomes will be documented and available to study staff.

Specific responsibilities of Investigators

1. *Awaiting approval.* An Investigator may determine whether potential subjects would be interested in participating in an investigation, but shall not request the written informed consent of any subject to participate, and shall not allow any subject to participate before obtaining IRB approval.
2. *Subject Qualification.* The Investigator is responsible for ensuring that all subjects entering the study conform to the patient selection criteria.
3. *Compliance.* An Investigator shall conduct an investigation in accordance with the signed agreement with the Sponsor, the investigational plan, all applicable FDA regulations, and any conditions of approval imposed by an IRB or FDA.

Investigator Records

A participating Investigator shall maintain the following accurate, complete, and current records relating to the Investigator's participation in an investigation for a period of 3 years after completion of the study:

1. All correspondence with another Investigator, an IRB, the Sponsor, or FDA, including required reports.
2. Records of each subject's case history and exposure to the device. Case histories include the case report forms and supporting data including, for example, signed and dated consent forms and medical records. Such records shall include:
 - a) Documents evidencing informed consent.
 - b) All relevant observations, including records concerning adverse device effects (whether anticipated or unanticipated), information and data on the condition of each subject upon entering, and during the course of, the investigation, including information about relevant previous medical history and the results of all diagnostic tests.
3. The protocol, with documents showing the dates have and reasons for each deviation from the protocol.
4. Any other records that FDA requires to be maintained by regulation or by specific requirement for a category of investigations or a particular investigation.

Investigator Reports

The Investigator shall prepare and submit the following complete, accurate, and timely reports:

1. *Unanticipated adverse device effects.* An Investigator shall submit to the Sponsor and to the reviewing IRB a report of any unanticipated adverse device effect occurring during an investigation as soon as possible, but in no event later than 10 working days after the Investigator first learns of the effect.
2. *Withdrawal of IRB approval.* An Investigator shall report to the Sponsor, within 5 working days, withdrawal of approval by the reviewing IRB of the Investigator's part of an investigation.
3. *Deviations from the investigational plan.* An Investigator shall document report to the Sponsor any deviation from the investigational plan.
4. *Informed consent.* If an Investigator enrolls a subject without obtaining informed consent, the Investigator shall report such use to the Sponsor and the reviewing IRB within 5 working days after the use occurs.
5. *Final report.* The Investigator shall complete a final report.
6. *Other.* The Investigator shall, upon request by a reviewing IRB, provide accurate, complete, and current information about any aspect of the investigation.

APPENDIX 3

Surgeon Survey

MRN _____

Date _____

Survey Respondent's Specialty (circle one): Neurologic Surgery / Neurology

Fluorescein Sodium (FS) Dose: _____ mg/kg IV

For the following questions, please record the time stamp at which the event occurred (e.g. 9:30 am):

1. Fluorescein Sodium Administered: _____ ; corresponding event (e.g. opening dura): _____
 - a. If second dose given, time administered: _____, dose _____ mg/kg
 - b. If third dose given, time administered: _____, dose _____ mg/kg
2. Tumor first visualized: _____
3. Did the contrast between the tumor and normal tissue **change after initial visualization of the tumor?**
No change in Contrast over Time / Increased Contrast over Time / Decreased Contrast over Time
4. If there was a change in contrast over time, **when did peak fluorescence** occur such that there was maximum contrast between the tumor and normal tissue? _____
5. Did the tissue become **saturated** with fluorescein such that there was no difference in the fluorescence of nerve and tumor? Yes / No
 - a. If so, when did saturation occur? _____
6. When did the fluorescence diminish such that it was no longer useful _____ / Not Applicable

For the following questions, please circle one number in the boxes below.

7. How well did fluorescence **correlate with your visual assessment** of the tumor and nerve tissue under normal microscopy without the Yellow 560 filter?

No correlation 1	Some correlation 2	Good correlation 3	Excellent correlation 4
---------------------	-----------------------	-----------------------	----------------------------

8. How well did fluorescence **correlate with electrostimulation** (e.g. tissues with high fluorescence do not stimulate, whereas nerve tissues with low fluorescence do stimulate)?

No correlation 1	Some correlation 2	Good correlation 3	Excellent correlation 4
---------------------	-----------------------	-----------------------	----------------------------

9. How helpful was the use of FS and Yellow 560 filter in.... (circle a rating for each row)

	Not helpful at all	Minimally helpful	Somewhat helpful	Very helpful	N/A
Distinguishing tumor from normal nerve	1	2	3	4	0
Preserving facial nerve function	1	2	3	4	0
Preserving hearing	1	2	3	4	0
Detecting residual tumor	1	2	3	4	0

10. Based on the use and performance of FS in this case alone, **how likely are you to use FS** in future cases involving this tumor type (excluding the research trial)?

Unsure 0	Plan to not use in any cases 1	Plan to use in select cases 2	Plan to use in the majority of cases 3	Plan to use in all cases 4
-------------	--------------------------------------	-------------------------------------	--	-------------------------------

Comments for the research team: _____

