3.1. Objectives

Primary objective of this initial feasibility study is to evaluate the benefit of using YE560 to visualize fluorescein sodium (FS) during surgery of VS, Meningioma, HNP, or HNS, determined from surgeon assessment.

Secondary objectives are:

- To evaluate the optimum FS dose and timing to be used with the YE560 device as determined by reported performance on surgeon surveys
- Quantify tissue differentiation of fluorescent VS and adjacent nerves using RGB image analysis
- To report clinical outcomes, including GTR rates, postoperative hearing outcomes, and postoperative facial nerve function

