3.4. Hypothesis

12. Given prior evidence of preferential uptake of FS in VS and meningiomas due to disrupted blood brain barrier, we hypothesize that use of intravenous FS will allow for visual differentiation of tumor and surrounding structures and nerves using YE560.
13. The optimal dosing for FS has not been established for this application. Pedro et al utilized 0.5-1.0 mg/kg body weight to visualize peripheral nerve sheath tumors with YE560. The authors found saturation of all tissues with 3-4 mg/kg dose within 18 seconds of administration. The blood-brain barrier may play a modulating role. Schebesch et al (2013) used 3-4 mg/kg to visualize malignant gliomas and observed fluorescence after 20-30 minutes. We suspect that the optimal dose will be 3-4 mg/kg, and peak fluorescence will take a similar amount of time. However, we will initially utilize 1.0 mg/kg SF administered at the time of first visualizing the tumor to enable subsequent doses (up to a maximum of 500 mg or 7 mg/kg). This will allow us

to determine the minimum effective dose and observe the time to peak fluorescence. The optimal dosing strategy will be finalized after the first 10 cases.

14. We hypothesize that the surgeons will be satisfied with the use of SF and YE560, as reflected in responses on the Surgeon Survey. Specifically, we hypothesize that greater than 75% of surgeons would choose to use SF and YE560 at least in the majority of future VS, meningioma, HNP, or HNS resections based on responses from the Surgeon Survey. Secondarily, we hypothesize that surgeons will rate the correlation of fluorescence with visual assessment with white light microscopy and electrostimulation to be “good” or “excellent” for over 75% of the cases.
15. Because the yellow fluorescence is primarily comprised of red and green components, we hypothesize that RGB component analysis of intraoperative images will yield significantly higher red and green values in the VS compared to the facial and cochlear nerves. Similar analysis may be conducted between the tumor and surround nerves or structures of interest for meningiomas, HNP, and HNS.

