3.6.11. Microscope imaging during YE560 fluorescence use

1. Standard methods of anesthesia as appropriate for open craniotomy or otologic surgery will be used.
2. Surgeons will gain access to the lesion of interest through a craniotomy or translabyrinthine approach.

3. At the time of tumor exposure, patients will be given intravenous FS. The timing and dose may vary. Maximum cumulative dose will not exceed 500 mg.

- Initial dosing protocol will be 1 mg/kg intravenous FS.
 - If insufficient fluorescence is obtained or washout occurs, additional doses of 1 mg/kg may be administered
- Based on the experience of the first 3 cases, modifications to the dosing protocol may be made.
 - A higher, single dose may be administered if there is insufficient fluorescence or premature washout. Additional doses may be given during surgery.
 - If saturation of normal tissue with fluorescence occurs, the dose may be decreased or the FS may be administered at an earlier time point (opening of dura, anesthesia induction, etc.) during subsequent cases
- Continued adjustments may be made to the dosing and timing, with a goal of standardizing the dose after 10 cases

4. Once the VS has been surgically exposed and FS has been administered, the YE560 fluorescence module shall be used to visualize fluorescence in the tissue. Images will be captured prior to tumor dissection, after exposure of the intracapsular tumor contents, and after maximum resection. A pair of images—one using the YE560 and one with white light microscopy—will be captured during each event.

5. With the YE560 turned on, images will be captured with the microscope. Video recording from the Pentero 900 and Kinevo 900 microscopes will be captured for the entirety of their use in the case.

6. The time from injection until to the point where the differential fluorescence is greatest will be recorded and documented in the surgeon's survey. Circulating nursing staff will record timestamps in collaboration with instruction from the operating surgeons.

7. The YE560 module will be applied during the aforementioned events and additionally at the discretion of the operating surgeons. Depending upon the number of potential regions identified for imaging and for possible biopsies, the YE560 fluorescence module is expected to add less than 10 minutes to the overall procedure.

8. At any time, the operating surgeon may turn off the YE560 module as dictated by the needs of surgery.

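### Survey item 6 gives one undefined answer to fluorescence that was never useful and fluorescence that never faded, and item 3 has no rise-then-fall category, so loss of usefulness cannot be summarised cleanly

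*Protocol*

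**What the plan says.** Protocol section 3.1 lists as a secondary objective: "To evaluate the optimum FS dose and timing to be used with the YE560 device as determined by reported performance on surgeon surveys". Appendix 3 is therefore the named source for dose and timing.

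The protocol expects a signal that develops and may then be lost. Section 3.4 starts with a low dose in order "to determine the minimum effective dose and observe the time to peak fluorescence", and it suspects a time to peak similar to the 20-30 minutes seen in a cited glioma series. Section 3.6.11 treats a weak signal and a fading signal as different events, either of which may lead to re-dosing: "If insufficient fluorescence is obtained or washout occurs, additional doses of 1 mg/kg may be administered". For later cases it adds: "A higher, single dose may be administered if there is insufficient fluorescence or premature washout". The goal is a standard dose after 10 cases.

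The form records this course as follows.

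- Item 1 takes the time of administration, with sub-items for second and third doses.
- Item 3 asks whether contrast changed after the tumour was first seen: "No change in Contrast over Time / Increased Contrast over Time / Decreased Contrast over Time".
- Item 4, asked only if there was a change, wants the time at which peak fluorescence did "occur such that there was maximum contrast between the tumor and normal tissue".
- Item 5 asks whether tissue became saturated, with the follow-up "If so, when did saturation occur".
- Item 6 asks "When did the fluorescence diminish such that it was no longer useful _____ / Not Applicable".

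Nothing on the form asks when the filter was last used.

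**The concern.** For choosing a dose, the best result on item 6 is fluorescence that outlasts the resection, and the worst is fluorescence that never helped. Neither has a fading time to enter, so both lead to the same *Not Applicable*. Section 3.6.11 names insufficient fluorescence and washout as separate reasons to change dosing, so the protocol itself needs the distinction that item 6 loses. Without an end-of-use time, a case that was still useful cannot be entered as censored from the form.

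Item 3 has a related gap. A rise followed by a fall is a likely course under the protocol's own expectations, yet it has no category. A surgeon who compares the start with the end may circle *No change* and then, following the condition on item 4, leave the peak time blank. Others may circle *Increased* or *Decreased* for the same course.

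At stake is a descriptive secondary result. With a standard dose intended after 10 cases, a few ambiguous records could weigh on the early reading.

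**Working it through.** The plan states no figure for useful duration, for the share of *Not Applicable* answers or for contrast patterns, so there is nothing to reproduce. The check has two parts.

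**1. Reading the form literally.**

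| Course in the case | Item 3 | Item 4 | Item 6 |
|---|---|---|---|
| Rises, peaks, fades | no matching category; one of three by judgement | completed if *Increased* or *Decreased*; may be skipped if *No change* | clock time |
| Useful until last filter use | any | as above | *Not Applicable* |
| Never useful | any | as above | *Not Applicable* |

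The last two rows cannot be told apart on item 6.

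**2. Direction of the error if duration is taken from recorded item 6 times alone.** Every input here is an assumption. Useful duration is exponential with mean *m* minutes among ever-useful cases, viewing ends at *C* minutes after injection, and a share *q* of cases is never useful.

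- Mean of recorded times, with all *Not Applicable* answers dropped: R = m − C / (e^(C/m) − 1).
- Mean useful time within the window among ever-useful cases: U = m(1 − e^(−C/m)).
- The same over all cases, with never-useful counted as zero: A = (1 − q)U.
- R equals A when q = 1 − R/U.

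For m = 120 and C = 240:

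- R = 120 − 240/6.389 = 82.4 min.
- U = 120 × 0.8647 = 103.8 min.
- The directions cross at q = 1 − 82.4/103.8 = 0.21.

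| m, C (min) | R | U | A at q = 10% | A at q = 30% | A at q = 50% | q at which R = A |
|---|---|---|---|---|---|---|
| 60, 240 | 55.5 | 58.9 | 53.0 | 41.2 | 29.5 | 6% |
| 120, 240 | 82.4 | 103.8 | 93.4 | 72.6 | 51.9 | 21% |
| 240, 240 | 100.3 | 151.7 | 136.5 | 106.2 | 75.9 | 34% |
| 240, 120 | 55.0 | 94.4 | 85.0 | 66.1 | 47.2 | 42% |

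R is below U in every row, because dropping cases that never faded removes the longest durations. Against A the sign depends on *q*: R is too short below the crossing point and too long above it.

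A second assumed model gives the same picture. Take a lognormal duration with log SD 0.6 and an end of viewing uniform between 60 and 240 min. For true medians of 60, 120 and 180 min among ever-useful cases, the recorded medians are about 55, 89 and 112 min. With 15% never useful, the all-case median is the quantile of the duration distribution at (0.50 − 0.15)/0.85 = 0.412. For a true median of 60 this is 60 × e^(−0.6 × 0.223) = 52.5 min, slightly below the recorded 55. For 120 and 180 it is 105.0 and 157.5 min, well above the recorded 89 and 112. With 5-15% never useful, *Not Applicable* covers about 16-25%, 44-50% and 65-69% of cases at the three medians.

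**The case against.** The strongest reply is that the survey as a whole records more than items 3 and 6 do singly, and that the protocol never promises a useful-duration result. Most of this stands, and it limits the point.

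- A reader might infer that the form cannot record a rise followed by washout. It can: *Increased* in item 3, a peak time in item 4 and a fading time in item 6. The instruction to circle one number is printed after item 6 and does not govern item 3. What is lost is a consistent category, together with a risk that item 4 is skipped.
- A reader might infer that the timing result as a whole is wrong. The measure named in section 3.6.11, time from injection to greatest differential fluorescence, comes from items 1 and 4. Item 6 plays no part in it, and item 3 touches it only through the skip.
- A reader might infer that useful duration is biased short. The protocol neither defines that quantity nor says that *Not Applicable* would be dropped, and the direction can reverse over all cases.
- A never-useful case will often show in items 5 and 7-10. Section 3.6.11 also provides for an image pair after maximum resection and for video of the whole microscope use.
- There are no dose arms, repeat doses make the time origin ambiguous, and the calculations above ignore re-dosing.

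The recovery argument is only partly met. Items 7-10 rate overall performance without a time, and the protocol describes no step for extracting an end-of-use time from video. A later analysis plan can set rules for *Not Applicable*, but it cannot restore from item 6 a distinction that item 6 did not collect.

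**Conclusion.** The defect is on the face of the form. Item 6 merges two opposite results and collects no end-of-use time, and item 3 lacks a category for a course the protocol expects. Loss of usefulness therefore cannot be summarised cleanly from the survey for the dose and timing objective. Any duration based only on recorded item 6 times would be too short among ever-useful cases, and too short or too long over all cases.

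The documents give nothing from which to size the error. The minutes and percentages above illustrate direction under assumed distributions and are not estimates for this trial. The point is a cheap improvement of minor priority to a descriptive secondary objective. The primary endpoint, item 10, is not affected.

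**What to change.** - **Item 6:** replace *Not Applicable* with two answers, *Never useful* and *Still useful at last YE560 view (time ___)*.
- **Item 3:** add *Increased, then decreased*.
- **Item 4:** ask for the peak time whenever contrast varied at any point.
- **If duration is summarised:** treat still-useful cases as censored at the last-view time. Report never-useful cases separately or as zero, and say which. State which administration time is the origin when doses were repeated.

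The cost is a one-page form revision and one extra time stamp, which the circulating staff who already record times can take. Forms completed before the change would need their stored video reviewed. No dosing or clinical rule changes.
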